### ***Bowel Cleansing Efficacy, Bowel Movement Kinetics, and Colonoscopy Results***

The primary endpoint of this study was the bowel cleansing efficacy assessed by the Boston bowel preparation scale (BBPS). The BBPS score is the sum of three segmental scores (range 0–9). Each segment is graded on a 4-point scale: 0, inadequate; 1, poor; 2, good; and 3, excellent. The rates of cleansing success, defined as all segments  $\geq 2$  and total BBPS score, were compared between groups. The bowel cleansing efficacy was also assessed by the Aronchick scale, which has scores of excellent, good, fair, poor, and very poor; details of the Aronchick scale are described elsewhere.

Bowel movement kinetics included the number of defecations, the start and finish time of bowel preparation, and the last defecation time. The amount of PEG and additional water ingested were recorded.

The results of the colonoscopy were analyzed. The cecal intubation time, colonoscopy withdrawal time, polyp detection rate (PDR), ADR, and the number of adenomas per patient

were recorded. For those who underwent EGD, fluid in the stomach was suctioned and its volume was measured.

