### ***Safety and Tolerability***

The composite safety profile included vital signs and questionnaire findings. Vital signs were checked on the day of randomization and at colonoscopy. Before the colonoscopy, all study subjects completed a questionnaire asking about adverse events, tolerability, and bowel movement kinetics. The questionnaire contained the following items: (1) adverse events related to the ingestion of the purgative; (2) number of sleep disturbances during the night before colonoscopy; (3) overall satisfaction with the bowel cleansing regimen (very satisfied, satisfied, intermediate, dissatisfied, very dissatisfied); and (4) willingness to use the bowel preparation regimen again. The patients used a checklist of possible adverse events to report whether they had experienced any of the following during or after ingestion of the bowel cleanser: nausea, vomiting, bloating, abdominal pain, dizziness, headache, and/or any other symptoms.

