### ***Statistical Analysis***

We assumed a bowel cleansing success rate for SPD of 85% and set the inferior margin at 10%. With 80% power and a type I error of 0.05, the required sample size for each group was calculated to be 158. A total of 176 subjects in each group was required, considering a 10% drop-out rate. Continuous variables are expressed as mean  $\pm$  standard deviation. Categorical variables are expressed as number and percent. The demographic characteristics, bowel cleansing efficacy, safety profile, tolerability, bowel movement kinetics, and results of colonoscopy were compared between the two groups. For this analysis, we used Student's *t* test for continuous variables, and the chi-square or Fisher's exact test for categorical variables. A *p*-value  $<0.05$  was considered significant. The safety analysis of safety and

tolerability included all subjects except those who were excluded for cancellation or protocol violation. Per-protocol (PP) analysis was used for the patients who completed colonoscopy. Bowel cleansing efficacy and bowel movement kinetics were investigated in the PP analysis. All statistical analyses were conducted using SAS software (9.0; SAS Institute, Cary, NC, USA).

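### Satisfaction and the Aronchick scale are ordered five-level secondary outcomes, but the only test named for categorical data ignores the order, costing up to about 20 points of power for a moderate consistent shift

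*Combined protocol and SAP*

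**What the plan says.** Three parts of the combined protocol and SAP bear on this.

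- **Safety and Tolerability** records overall satisfaction on five levels: "very satisfied, satisfied, intermediate, dissatisfied, very dissatisfied".
- **Bowel Cleansing Efficacy, Bowel Movement Kinetics, and Colonoscopy Results** adds the Aronchick scale to the BBPS as a further cleansing measure, "which has scores of excellent, good, fair, poor, and very poor".
- **Statistical Analysis** states that "bowel cleansing efficacy, safety profile, tolerability, bowel movement kinetics, and results of colonoscopy were compared between the two groups". It then gives two rules: "Student's *t* test for continuous variables", and "the chi-square or Fisher's exact test for categorical variables". A p-value below 0.05 "was considered significant".

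No rank, trend or ordinal-model method appears. The plan assigns no test to either scale by name, does not say whether levels are scored or collapsed, and gives no expected distribution, effect size or power for them.

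**The concern.** Worded grades fall naturally under the categorical rule. A chi-square test on a table of two groups by five levels has (2 − 1) × (5 − 1) = 4 degrees of freedom. It spreads its sensitivity over every possible pattern of difference and takes no account of which level is better. Fisher's exact test on the same table also ignores the order. A rank or mean-score test puts one degree of freedom on the question of interest, namely whether answers under one regimen sit higher on the scale.

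Two things are at stake for these secondary outcomes. A moderate real shift could be reported as non-significant when an ordered test on the same data would have found it. And a significant 4-df result does not by itself say which regimen did better.

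**Working it through.** **1. The plan's own figure.** The sample size rests on BBPS cleansing success: 85% in both groups, margin 10 points, "With 80% power and a type I error of 0.05".

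n per group = (1.645 + 0.842)² × 2 × 0.85 × 0.15 / 0.10² = 6.183 × 0.255 / 0.01 = 157.7, so 158. With 10% drop-out, 158 / 0.90 = 175.6, so 176.

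Both stated figures reproduce with 0.05 taken as one-sided (one-sided 0.025 would give 201 and 224). The plan has no power figure for the ordinal scales to reproduce. Below, 158 per group is used with a two-sided 0.05 level; the two-sided level is an assumption.

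**2. Analytic comparison.** If the ordered test captures the whole effect, 80% power on 1 df needs a noncentrality of (1.960 + 0.842)² = 7.85. A 4-df chi-square with the same noncentrality has 59.5% power, a loss of 20.5 points. To regain 80%, it would need about 1.52 times the sample: 1.52 × 158 = 240 per group.

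**3. A worked shift.** Assume 20% in each level in one group and a proportional-odds shift of 1.75.

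- Cumulative odds 0.25, 0.667, 1.5 and 4 become 0.4375, 1.167, 2.625 and 7.
- The level proportions become 30.4, 23.4, 18.6, 15.1 and 12.5%.
- Chi-square noncentrality is n × Σ(p₀ − p₁)²/(p₀ + p₁) = 158 × (0.0216 + 0.0027 + 0.0005 + 0.0069 + 0.0173) = 158 × 0.0490 = 7.74.

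That is close to the 7.85 in step 2, so powers near 59% and 80% are expected. The simulation in step 4 gives 59.0% and 79.9%.

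**4. Simulation.** 20,000 trials per setting, 158 per group, Pearson chi-square against the tie-corrected Wilcoxon rank-sum test. All distributions and odds ratios are assumptions. Entries are chi-square % / rank-sum % (gap in points).

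| Assumed levels (%) | OR 1.0 | OR 1.3 | OR 1.5 | OR 1.75 | OR 2.0 | OR 2.5 | OR 3.0 |
|---|---|---|---|---|---|---|---|
| 20/20/20/20/20 | 5.1/5.1 | 15.4/25.9 (10.5) | 32.9/52.7 (19.8) | 59.0/79.9 (20.9) | 79.9/93.6 (13.7) | 97.0/99.6 (2.6) | 99.6/100 (0.4) |
| 10/25/30/25/10 | 4.6/4.6 | 15.2/25.7 (10.5) | 32.4/52.3 (19.9) | 58.2/78.8 (20.6) | 79.1/92.7 (13.6) | 96.4/99.4 (3.0) | 99.7/100 (0.3) |
| 30/40/20/7/3 | 4.7/4.7 | 14.1/24.6 (10.5) | 29.8/49.6 (19.8) | 55.3/76.8 (21.5) | 76.0/91.3 (15.3) | 95.5/99.2 (3.7) | 99.3/99.9 (0.6) |
| 45/40/10/4/1 | 4.1/5.0 | 13.1/23.9 (10.8) | 27.8/47.2 (19.4) | 51.0/73.0 (22.0) | 72.2/89.0 (16.8) | 93.2/98.6 (5.4) | 98.6/99.9 (1.3) |
| Three levels: 45/40/15 | 5.0/5.1 | 17.8/23.1 (5.3) | 37.2/46.8 (9.6) | 62.8/73.0 (10.2) | 81.5/88.6 (7.1) | 96.8/98.5 (1.7) | 99.6/99.9 (0.3) |

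At 176 per group the five-level gaps are similar: 20.0 to 21.2 points at OR 1.5 and 10.5 to 14.4 at OR 2.0.

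**5. Where chi-square does better.** With 20% in each level against an assumed U-shaped 28/16/12/16/28%, chi-square has 65.4% power and rank-sum 5.4%.

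**The case against.** The strongest case on the other side has four parts.

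- **The assignment is inferred.** The section states a general rule and never names the two scales. A t test on numeric scores, or collapsing levels, is not excluded. This stands as a limit on certainty. At OR 1.75 with evenly used levels, a t test on scores has 79.8% power against 79.9% for rank-sum, so under that reading almost nothing is lost. With the 45/40/10/4/1% distribution it has 67.8% against 73.0%. Collapsing is less safe: comparing the top two levels with the rest gives 69.5% and 36.1% in those two settings. Naming the test settles the matter whichever was meant.
- **The loss is not a fixed 20 points.** A reader might infer a flat figure from the 80% reference point. The documents do not support that, because they give no distribution or effect size. Twenty points is near the peak of a range that falls to about 1 point or less.
- **The advantage depends on a consistent shift.** This stands, as the U-shaped example shows. A common odds ratio also relies on proportional odds, so that assumption needs checking.
- **Chi-square is valid and the outcomes are secondary.** This stands. The gain is in efficiency; no error rate is being corrected.

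A reader might also infer that a weak test on satisfaction helps the noninferiority claim. It does not: the sample size and margin concern the cleansing success rate, and satisfaction has no margin and no part in that conclusion. Nor do the documents say that tolerability is expected to differ between the regimens. The plan's lack of effect estimates with intervals applies to all its comparisons and is not caused by chi-square.

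**Conclusion.** The point holds as a conditional loss of efficiency. On the natural reading, two ordered five-level secondary outcomes are compared with a test that ignores their order. For a consistent proportional-odds shift at 158 per group with all five levels in use, the loss is 19 to 22 points at OR 1.5 to 1.75, 10 to 11 at OR 1.3, 14 to 17 at OR 2.0, 3 to 5 at OR 2.5 and about 1 or less at OR 3.0. With three levels in use it is about 10 at most. These sizes rest on assumed distributions, assumed odds ratios and a two-sided 0.05 level.

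It would be wrong to conclude that the planned test is invalid, that the loss is always 20 points, or that the primary BBPS noninferiority result or its sample size is affected. The change is still worth making, because the gain is real for the most plausible kind of difference on an ordered scale and costs almost nothing.

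**What to change.** Add one sentence to Statistical Analysis covering satisfaction and the Aronchick scale:

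- Compare them with the Wilcoxon rank-sum test, or with the Cochran-Mantel-Haenszel row-mean-score test stratified by colonoscopy time and sex, the randomization factors given under Study Population and Protocol.
- Report a common odds ratio with 95% CI after checking proportional odds.
- Show the frequency table by level and group.
- Keep chi-square or Fisher's exact test for binary and unordered outcomes.

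The methods are available in standard SAS procedures. No extra subjects or data are needed, and the primary analysis does not change. The one statistical cost is low sensitivity to a non-monotone difference, which chi-square would detect better and the frequency table would still show. The section is written in the past tense. If results have already been seen, present the ordered analysis as a labelled addition beside the chi-square result, so that it does not look like a test chosen afterwards.

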## **MATERIALS AND METHODS**

### ***Study Population and Protocol***

This was a single-center, prospective, assessor-blinded, noninferiority, randomized controlled study conducted at a tertiary referral center (Incheon St. Mary's Hospital, Incheon, Korea). Individuals who underwent colonoscopy with or without esophagogastroduodenoscopy (EGD) for various indications were eligible for inclusion. Study subjects were enrolled between November 2017 and February 2018. Individuals who met all of the following criteria were included: (1) age 40–75 years; (2) American Society of Anesthesiologists (ASA) class I or II; (3) outpatients; and (4) no previous history of bowel resection or gastrectomy. Exclusion criteria were as follows: (1) cancellation, (2) violation of protocol for bowel preparation, such as subjects in the SDD group ingesting a purgative the previous day or as an SPD; or subjects in the SPD group ingesting a purgative the previous day or as an SDD. After informed consent was obtained, study subjects were randomly assigned to the SDD or SPD group. Randomization was performed using a block size of four, stratified by colonoscopy time (morning vs afternoon) and sex, using a computer-generated randomization list.

The protocol for bowel preparation is shown in Figure 1. Subjects underwent bowel preparation at home. Study subjects were encouraged to finish 2 L PEG within 1 h. If ingestion was difficult, 2 L PEG was consumed within 1.5 h. Hence, 2 to 3 h were required to fully ingest the 4 L PEG. Individuals in the SDD group ingested PEG on the day of the colonoscopy. For those who underwent morning colonoscopy, ingestion of 4 L PEG was started at 5 a.m. Individuals who were scheduled to undergo afternoon colonoscopy were instructed to take 2 L PEG starting at 7 a.m., then after a 2-h break, the remaining 2 L PEG was ingested starting at 10 a.m. Individuals in the SPD were instructed to begin ingesting 2 L

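### As described, the adverse-event checklist records whether each symptom occurred but not how severe it was, so the SDD versus SPD adverse-event comparison reflects frequency only

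*Combined protocol and SAP*

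**What the plan says.** Under Safety and Tolerability, adverse events are self-reported on a questionnaire filled in before colonoscopy: "The patients used a checklist of possible adverse events to report whether they had experienced any of the following". The reporting period covers the drinking of the purgative and the time afterwards. The listed items are "nausea, vomiting, bloating, abdominal pain, dizziness, headache, and/or any other symptoms". No grade, duration or number of episodes is mentioned for any of them.

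The same questionnaire has three other items: "number of sleep disturbances during the night before colonoscopy", "overall satisfaction with the bowel cleansing regimen (very satisfied, satisfied, intermediate, dissatisfied, very dissatisfied") and "willingness to use the bowel preparation regimen again". Vital signs are taken at randomization and at colonoscopy. The section on bowel cleansing efficacy and kinetics adds the amounts of PEG and extra water taken.

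The Statistical Analysis section compares safety and tolerability between groups, using "the chi-square or Fisher's exact test for categorical variables" and Student's t test for continuous ones. It defines no severity outcome and no per-subject symptom summary.

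On the schedules, Study Population and Protocol says that for SDD with a morning colonoscopy "ingestion of 4 L PEG was started at 5 a.m". SDD with an afternoon colonoscopy takes 2 L from 7 a.m. and 2 L from 10 a.m., with a stated two-hour pause. SPD takes 2 L from 9 p.m. the evening before and 2 L on the day, from 7 a.m. or 10 a.m.

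**The concern.** Both arms drink the same 4 L. What differs is how the volume is spread over time, and the contrast is sharpest for morning colonoscopy. There, SDD takes everything in one sitting of 2 to 3 hours, while SPD has a night between the halves. Such a contrast could change how bad nausea, bloating or vomiting is, as well as how many subjects have it. A tick for slight bloating and a tick for severe bloating count the same, so a pure change in severity leaves the adverse-event table unchanged at any sample size.

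If cleansing proves noninferior, readers are likely to look to safety and tolerability when comparing the schedules. That is an inference about how the results would be used; the plan does not state it. Severity that is not asked for at the time cannot be reconstructed later.

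**Working it through.** **The plan's own figure.** The only sample-size figure concerns the primary endpoint. With 85% success in both arms, a 10-point margin, one-sided alpha 0.05 and 80% power:

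n = (1.645 + 0.842)² × 2 × 0.85 × 0.15 / 0.10² = 6.18 × 0.255 / 0.01 ≈ 158 per group.

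With 10% dropout, 158 / 0.90 = 175.6, so 176. Both figures reproduce. They do not bear on this point beyond supplying n = 158 per arm.

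**What the text supports.** The satisfaction item has all its response levels written out, and so do the cleansing scales. The symptom items have none. The natural reading is presence or absence.

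**What yes/no data can and cannot show.** The documents give no symptom rates, so every rate below is an assumption. The test is two-sided at 5% with n = 158 per arm, and

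power ≈ Φ[(d − 1.96·s₀)/s₁], where d = |p₁ − p₂|, s₀ = √(2p̄(1 − p̄)/n) and s₁ = √(p₁(1 − p₁)/n + p₂(1 − p₂)/n).

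1. *Severity shift only.* Any nausea is 40% in both arms; moderate-or-severe is 10% (SPD) versus 20% (SDD).
   - Yes/no: d = 0, so rejection is at the 5% error rate.
   - Moderate-or-severe: d = 0.10, s₀ = 0.0402, s₁ = 0.0398. (0.10 − 0.0788)/0.0398 = 0.53, giving about 70%. Simulation gives about 71%.
2. *Small frequency shift plus the same severity shift.* Any nausea 40% versus 45%; moderate-or-severe 10% versus 20%. Yes/no about 15%; moderate-or-severe about 70 to 72%.
3. *Uniform shift over all grades, odds ratio 1.7.* Start from none/mild/moderate/severe = 60/25/10/5%.
   - Any nausea: odds 0.40/0.60 × 1.7 = 1.133, so 40% versus 53.1%. Yes/no power about 65%.
   - Moderate-or-severe: odds 0.15/0.85 × 1.7 = 0.30, so 15% versus 23.1%. Power about 45%.
4. *Rarer severe symptoms.* Equal frequency of 20%, 30% or 40%, with a severe share of 20% versus 40% among those affected. The graded contrasts are 4% versus 8%, 6% versus 12% and 8% versus 16%, with power about 32%, 46% and 59%. Yes/no stays at 5%.

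**Would one worst-grade summary per subject do the job?** Suppose only nausea worsens (moderate-or-severe 10% versus 20%), and the other six items (five named plus the open category) each have the same moderate-or-severe rate q in both arms. With independent items the proportions are 1 − 0.9(1 − q)⁶ and 1 − 0.8(1 − q)⁶.

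| q | SPD | SDD | difference | power |
|---|---|---|---|---|
| 3% | 25.0% | 33.4% | 8.3 points | 37% |
| 5% | 33.8% | 41.2% | 7.4 points | 27% |
| 10% | 52.2% | 57.5% | 5.3 points | 16% |

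Correlation between items of up to 0.5 gives about 34–37%, 24–27% and 12–16% for the three rows. If three symptoms worsen together, power is about 52–74%, again under assumed rates. The 71% for a single graded symptom therefore does not carry over to a worst-grade summary.

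**The case against.** A reader might infer that a harsher regimen would come out as equally well tolerated. The documents do not support that. Tolerability is also judged by five-level satisfaction, willingness to repeat and the count of sleep disturbances; vital signs and PEG volume taken are recorded too. A regimen with clearly worse symptoms could show in several of these. What remains is that none identifies a symptom, that satisfaction and willingness also take in convenience and hour of waking, and that a 5 a.m. start can disturb sleep in its own right.

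A reader might also infer that the form itself has only yes/no boxes. The text is a short summary of a questionnaire drawn from cited sources, and the form is not reproduced. The supportable statement is that no grading is described. Nor does the plan say in so many words that symptoms are tested one by one.

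The schedule contrast should not be overdrawn. Afternoon SDD has a two-hour pause, and the same drinking pace is advised to subjects generally. That severity would shift without frequency is plausible, but nothing in the documents shows it.

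Finally, the first numerical example holds frequency equal by construction, so yes/no must sit at 5%; under a uniform shift yes/no is the better measure. This stands, and it is why the yes/no rates must be kept and why moderate-or-severe should not displace them.

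**Conclusion.** The point holds in a limited form. As the plan is written, the adverse-event comparison measures how often symptoms occur and not how severe they are; the other tolerability measures are only indirect signals of severity. How much this costs depends on assumed rates. For a single symptom it runs from a large loss (about 5% versus 71% detection for a pure severity shift from 10% to 20%) to none (yes/no ahead, about 65% versus 45%, under a uniform shift). With rarer severe symptoms, grading would reach only about 32–59%.

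This is a cheap improvement to secondary safety and tolerability data. It does not touch the primary endpoint, the margin or the sample size.

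**What to change.** - On the same pre-colonoscopy checklist, replace each tick with none, mild, moderate or severe. If the form already grades symptoms, say so in the plan and analyse the grades.
- Keep the yes/no rate for each symptom.
- Add, for each symptom, the proportion graded moderate or severe in each arm, as a difference (SDD minus SPD) with 95% CI.
- A worst-grade-per-subject summary may be given as supportive. It should not lead, because it dilutes a difference confined to one symptom, and its moderate-or-severe cut is less powerful than yes/no under a uniform shift.
- Where only ticks were collected, state in the report that the adverse-event comparison concerns frequency and leaves severity unassessed.

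The cost is a slightly longer form and one extra table, with no added visits, staff or subjects. There are two drawbacks. Six named symptoms plus the open category add seven secondary comparisons, which should be read as descriptive. The grades are also self-rated by subjects who know their regimen, as the present items already are.

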### ***Statistical Analysis***

We assumed a bowel cleansing success rate for SPD of 85% and set the inferior margin at 10%. With 80% power and a type I error of 0.05, the required sample size for each group was calculated to be 158. A total of 176 subjects in each group was required, considering a 10% drop-out rate. Continuous variables are expressed as mean  $\pm$  standard deviation. Categorical variables are expressed as number and percent. The demographic characteristics, bowel cleansing efficacy, safety profile, tolerability, bowel movement kinetics, and results of colonoscopy were compared between the two groups. For this analysis, we used Student's *t* test for continuous variables, and the chi-square or Fisher's exact test for categorical variables. A *p*-value  $<0.05$  was considered significant. The safety analysis of safety and

tolerability included all subjects except those who were excluded for cancellation or protocol violation. Per-protocol (PP) analysis was used for the patients who completed colonoscopy. Bowel cleansing efficacy and bowel movement kinetics were investigated in the PP analysis. All statistical analyses were conducted using SAS software (9.0; SAS Institute, Cary, NC, USA).

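### One unadjusted p<0.05 rule covers about 24 non-primary outcomes, with no testing order and no exploratory label

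*Combined protocol and SAP*

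**What the plan says.** The Statistical Analysis section gives one sentence on scope: "The demographic characteristics, bowel cleansing efficacy, safety profile, tolerability, bowel movement kinetics, and results of colonoscopy were compared between the two groups". It assigns Student's t test "for continuous variables, and the chi-square or Fisher's exact test for categorical variables", and a p-value below 0.05 "was considered significant". The sentence covers six families of comparison, one of them baseline demographics.

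The variables behind those families are named in two earlier sections.

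- Bowel Cleansing Efficacy, Bowel Movement Kinetics, and Colonoscopy Results makes cleansing efficacy on the Boston scale (BBPS) the primary endpoint, compared as a success rate and as a total score. It adds a second scale: "The bowel cleansing efficacy was also assessed by the Aronchick scale". On kinetics it says: "Bowel movement kinetics included the number of defecations, the start and finish time of bowel preparation, and the last defecation time". PEG and water intake follow. The colonoscopy results are "The cecal intubation time, colonoscopy withdrawal time, polyp detection rate (PDR), ADR, and the number of adenomas per patient", plus gastric fluid volume in those who had upper endoscopy.
- Safety and Tolerability lists vital signs, sleep disturbance, satisfaction, willingness to repeat, and a checklist of "nausea, vomiting, bloating, abdominal pain, dizziness, headache, and/or any other symptoms".

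The document does not order these comparisons, make them depend on the noninferiority result, adjust for their number, or describe them as exploratory or descriptive.

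**The concern.** A noninferiority result on cleansing shows only that SDD is not unacceptably worse than the split regimen (SPD). A reader who wants a reason to prefer SDD will look to the other outcomes, and the plan lets any of them be reported as significant on the same footing. A planned advantage then cannot be told apart from the best of many unplanned ones, and an isolated significant result on tolerability or detection is weak evidence.

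The same threshold also applies to demographics. Allocation was random, so the null there is true by construction apart from the exclusions made after randomisation. A p-value tells the reader little in that setting.

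**Working it through.** **The plan's own figure.** The document states no family-wise error rate. Its only error-rate calculation is the sample size. With 85% success in both groups, a margin of 10 points, 80% power and one-sided 0.05:

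n = (1.645 + 0.842)² × 2 × 0.85 × 0.15 / 0.10² ≈ 158 per group, and 158 / 0.90 = 175.6, so 176.

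Both stated figures reproduce. That calculation concerns cleansing success alone and allows for no other test.

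**Count of other outcomes** (cleansing success left out):

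- total BBPS and Aronchick: 2
- defecations, start time, finish time, last defecation time: 4
- PEG and water intake: 2
- cecal intubation time, withdrawal time, PDR, ADR, adenomas per patient: 5
- gastric fluid volume: 1
- adverse-event items (six named, plus any other): 7
- sleep disturbance, satisfaction, willingness: 3

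Total: 2 + 4 + 2 + 5 + 1 + 7 + 3 = 24. Vital signs (number of items not stated) and demographics are not counted.

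**At least one false positive in either direction, all nulls true, independent tests.** The formula is 1 − 0.95^k. The sidedness of 0.05 is not stated for these tests; two-sided is assumed.

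- k = 24: 1 − 0.95²⁴ = 0.708, with 24 × 0.05 = 1.2 false positives expected
- k = 23 (start time removed): 0.693, with 1.15 expected
- k = 22 (start and finish time removed): 0.677

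**Allowing for correlation.** The document gives no correlations, so these are assumptions. Two-sided z tests were simulated under the global null, 200,000 runs each.

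- 24 tests, correlated only within domains at 0.3, 0.5 and 0.7: 0.68, 0.64 and 0.58
- 22 tests, 0.7 within and 0.2 between domains: 0.53
- 24 tests, equal correlation across all outcomes of 0.3, 0.4 and 0.5: 0.59, 0.53 and 0.46

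The last value matches 12 independent tests: 1 − 0.95¹² = 0.460. Still stronger correlation across every outcome lowers the figure further (0.39 at 0.6 and 0.31 at 0.7), but it would have to hold between outcomes as unlike as withdrawal time and headache.

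**At least one false positive favouring SDD.** Only one tail counts, 0.025 per test. The outcomes that could most plausibly support a preference are the 7 adverse-event items, the 3 questionnaire items, and PDR, ADR and adenomas per patient: 7 + 3 + 3 = 13.

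1 − 0.975¹³ = 0.280 if independent. The true figure is lower if the outcomes are correlated, as the three overlapping detection measures will be.

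**Effect of Fisher's test.** Its actual size at 158 per group was computed as 0.013 to 0.038 for event rates of 2% to 30%. Using 0.03 for the seven adverse-event items gives 1 − 0.95¹⁷ × 0.97⁷ = 0.66 for all 24 in either direction.

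**The case against.** A reader might infer that the trial is about as likely as not to produce a false claim in favour of SDD. The document does not support that, for three reasons.

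- The 45-70% range counts false positives in both directions and over all 24 outcomes. Many of these, such as water volume or withdrawal time, are process measures and not obvious grounds for choosing a regimen. For the 13 outcomes that are, the figure is about 28% at most.
- The global null does not hold throughout. SPD starts at 9 p.m. the day before, so start time differs by design. In the morning stratum SDD should finish about 7 to 8 a.m. (5 a.m. plus 2 to 3 h) and SPD about 8 to 8:30 a.m. (7 a.m. plus 1 to 1.5 h), so finish time differs too. Last defecation time and sleep disturbance may also truly differ. A significant result on these would not be a false claim.
- The document never says that a significant secondary result will be used to support one regimen over the other.

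A reader might also infer that the primary conclusion is at risk from these tests. It is not: success on the other outcomes is no route to declaring noninferiority of cleansing success, so their number does not change its type I error.

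These objections narrow the point without removing it. The plan still attaches the unqualified word significant to every comparison, and nothing else in the document limits how such a result may be read.

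**Conclusion.** The point holds as a modest improvement to the wording. One unadjusted threshold covers 24 named non-primary outcomes, plus vital signs and demographics, with no order and no exploratory label.

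If all nulls were true, at least one false positive in either direction would have a chance of about 70% under independence, and roughly 45-70% for the assumed correlation patterns up to 0.5 across all outcomes. At least one favouring SDD among the 13 tolerability and detection outcomes would have a chance of about 28% if independent, and lower otherwise. These figures rest on two-sided tests, on true nulls that do not hold for some timing outcomes, and on correlations that the document does not supply.

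**What to change.** In the Statistical Analysis section:

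1. Reserve significant, or any confirmatory wording, for noninferiority of cleansing success.
2. State that all other outcomes are exploratory. Report each as a between-group difference with a 95% confidence interval and no significance label.
3. Describe demographics by group without p-values.

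A single secondary outcome tested only after noninferiority is shown would take no alpha from the primary comparison. It is valid only if that outcome was named before outcome data were seen. The document describes enrolment as complete and names no such outcome, so choosing one now could not be presented as prespecified. The noninferiority test or interval on which such a sequence would depend would also have to be written down, since the section names only t, chi-square and Fisher tests.

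The cost is a few sentences, with no new data or patients. The downside is that secondary results can no longer be called significant.
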